8.1.2 Definition of Serious Adverse Events (SAE)

If an AE meets any of the following criteria, it is to be reported to the Sponsor's Safety department and Pharmacovigilance as a serious adverse event (SAE) using SAE report form within 24 hours of occurrence or notification to the study site:

Death of Subject	An event that results in the death of a subject.
Life-Threatening	An event that, in the opinion of the Investigator, would have resulted in immediate fatality if medical intervention had not been taken. This does not include an event that would have been fatal if it had occurred in a more severe form.
Hospitalization	An event that results in an admission to the hospital for any length of time. This does not include an emergency room visit or admission to an out-patient facility.
Prolongation of Hospitalization	An event that occurs while the study subject is hospitalized and prolongs the subject's hospital stay.
Congenital Anomaly/birth defect	An anomaly detected at or after birth or any anomaly that result in fetal loss.
Persistent or Significant Disability/Incapacity	An event that results in a condition that substantially interferes with the activities of daily living of a study subject. Disability is not intended to include experiences of relatively minor medical significance such as headache, nausea, vomiting, diarrhea, influenza, and accidental trauma (e.g., sprained ankle).
Other Important Medical Event	An important medical event that may not be immediately life-threatening or result in death or hospitalization, but based on medical judgment may jeopardize the subject and may require medical or surgical intervention to prevent any of the outcomes listed above (i.e., death of subject, life- threatening, hospitalization, prolongation of hospitalization, congenital anomaly, or persistent or significant disability/incapacity). Examples of such events include allergic bronchospasm requiring intensive treatment in an emergency room or at home, blood dyscrasias or convulsions that do not result in inpatient hospitalization, or the development of drug dependency or drug abuse.

8.1.3 Definition of Unanticipated Problems

An Unexpected Adverse Event is any AE that is not identified in nature, severity, or frequency in the current Investigator's Brochure or product information.

A Serious and Unexpected Suspected Adverse Reaction (SUSAR) is any suspected adverse reaction to the study product that is both serious and unexpected.

8.2 Classification of an Adverse Event

8.2.1 Severity of Event

The Investigator will use the following definitions to rate the severity of each AE and SAE:

Mild The event is transient and easily tolerated by the subject.

Moderate The event causes the subject discomfort and interrupts the subject's usual activities.

Severe The event causes considerable interference with the subject's usual activities and may be

incapacitating or life-threatening.

8.2.2 Relationship to Study Drug

The Investigator will use the following definitions to assess the relationship of the AE/SAE to the use of investigational product:

Definitely Related The event occurred within a reasonable time after drug administration or drug

concentration and body fluids demonstrated that the study drug was present: the event could not be reasonably explained by known characteristics including concomitant

therapies; the adverse event abated after discontinuing the study drug.

Probably Related The event has a strong temporal relationship to study drug or recurs on re-challenge and

another etiology is unlikely or significantly less likely.

Possibly Related The event has a strong temporal relationship to the study drug and an alternative etiology

is equally or less likely compared to the potential relationship to study drug.

Probably Not Related The event has little or no temporal relationship to the study drug and/or a more likely

alternative etiology exists.

Not Related The event is due to an underlying or concurrent illness or effect of another drug and is not

related to the study drug (e.g., has no temporal relationship to study drug or has a much

more likely alternative etiology).

If an Investigator's opinion of not related to study drug is given, an alternate etiology must be provided by the Investigator for the AE.

8.2.3 Expectedness

The Principal Investigator will be responsible for determining whether an AE is expected or unexpected. An AE will be considered unexpected if the nature, severity, or frequency of the event is not consistent with the risk information previously described for the study agent.

8.3 Time Period and Frequency for Event Assessment and Follow-Up

The Investigator will monitor each subject for clinical evidence of adverse events on a routine basis throughout the study. Any AE/SAE prior to the Baseline visit will be considered past medical history (PMH). The AE reporting period for this study begins upon receiving the first application of investigational product and ends at the final protocol required visit. SAE(s) that are observed or spontaneously reported during the subject's participation in the trial will be captured and monitored until the Investigator deems the event to be chronic or not clinically significant or the subject to be stable.

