2.3.2 Known Potential Benefits

The adverse event profile observed reveals a product safe for use in children as young as 6 months. The demonstration of efficacy with a single 10-minute treatment is unique amongst anti-lice products and will likely improve compliance. Ivermectin 0.5% lotion represents a significant addition to the current armamentarium for the treatment of head lice.

This medication is widely used and prescribed because the benefits associated with the use of it is greater than the risk of the side effects. Ivermectin 0.5% lotion has demonstrated robust efficacy in comparison to placebo with a single 10-minute treatment for head lice in subjects 6 months of age and older.

3 Objectives and Purpose

The primary objective of the study is to establish the efficacy of a single application of Ivermectin 0.5% lotion in the treatment of head lice under at-home use conditions compared with Sklice® 0.5% lotion, and to demonstrate that both active lotions have superior efficacy compared to Placebo.

The secondary objective of the study is to demonstrate the safety and local tolerability of Ivermectin 0.5% lotion compared with Sklice® 0.5% lotion.

4 Study Design and Endpoints

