4.1 Description of the Study Design

This is a Phase 3 Randomized, Multi-Center, Double-blind, Placebo Controlled, Parallel Group Trial to Evaluate Efficacy and Safety of Mayne Pharma's Ivermectin 0.5% Lotion Compared to Sklice® 0.5% Lotion in the Treatment of Head Lice. The subject population includes healthy male and female subjects aged 6 months through 18 years who are infested with *Pediculus humanus capitis*. The youngest infested household member will be considered the index subject. Household members, up to a maximum of 3 members, infested with an active head lice infestation defined as at least 1 live louse (adult and/or nymph) present on the scalp and/or hair, as determined by a trained evaluator will receive treatment with an over-the-counter head lice treatment product at baseline.

The planned overall sample size for this clinical trial is approximately 280 index subjects, who will be randomized at different geographical clinical research centers in the United States.

Potential subjects will be screened and the index subject will be eligible for enrollment into the study. During the baseline visit (Day 1), which can occur on the same day as screening (Day 0), the Investigator will record subject's demographics, medical history, review concomitant medication, identifying any prohibited therapies the subject may receive, perform physical examination, collect vital signs and perform urine pregnancy test. Eligible subjects will be randomized in a ratio of 3:3:1 to receive either the Mayne Pharma's Ivermectin 0.5% lotion, Sklice® 0.5% lotion, or placebo lotion treatment and will be trained on the application of the study drug and subject's diary completion. Infested household members, up to 3 members per household, will be treated with an over-the-counter head lice treatment product on-site.

The study drug will be applied as a single, at-home dose. Subjects will be instructed to apply a full tube amount (4 oz.) of Ivermectin 0.5% lotion to fully coat dry hair and scalp, avoiding the eyes and mucus membranes. The lotion will be left on the hair and scalp for 10 minutes, then rinsed off with warm water. The tube is intended for a single use; all used tubes should be returned at the second visit (first follow-up visit) to the clinical site for product accountability. In addition to receiving the study drug, the index subjects and household members will be instructed on an overall lice management program, which includes:

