7.3.3 Follow-up

Follow-up Visit Day 2 (Visit 3) (+/- 1 Day)

- Record adverse events as reported by participant or observed by investigator.
- Collect used test tube product from index subject.
- Concomitant and prohibited medication review.
- Perform assessment for living head lice on index subject for visual confirmation of infestation for a minimum of 15 minutes.
- If active lice are present on index subject, provide Standard of Care and withdraw the subject from the study.
- Record Subject Self-Assessment for index subjects.
- Perform skin/scalp irritation and ocular irritation for index subjects and record results on Site Assessment form.
- Record index subject's adherence to treatment program through collection of subject diary.
- Inform index subject when to come back for their follow-up visit.

Follow-up Visit Day 8 (Visit 4) (+/- 2 day)

- Record adverse events as reported by participant or observed by investigator.
- Concomitant and prohibited medication review.
- Perform assessment for living head lice on index subject for visual confirmation of infestation for a minimum
 of 15 minutes.
- If active lice are present, provide Standard of Care and withdraw the subject from the study.
- Record Subject Self-Assessment for index subjects.
- Perform skin/scalp irritation and ocular irritation for index subjects and record results on Site Assessment form.
- Inform index subject when to come back for their final study visit.

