7.6 Rescue Medications, Treatments, and Procedures

If live lice are present on Day 2, Day 8 or Day 15, the subject will receive an over-the-counter (OTC) rescue treatment for head lice and their study participation will be considered complete and will be considered a treatment failure, with subjects to be considered in both the mITT and PP population.

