8.1 Specification of Study Parameters

The Investigator will monitor each subject for clinical evidence of adverse events on a routine basis throughout the study. The Investigator will assess and record any AE in detail including the date of onset, description, severity, time course, duration and outcome, relationship of the adverse event to study drug, an alternate etiology for events not considered "related" or "probably related" to study drug, final diagnosis, if known, and any action(s) taken. For AEs to be considered intermittent, the events must be of similar nature and severity and each intermittent AE will be reported separately. AEs and SAEs, whether in response to a query, observed by site personnel, or reported spontaneously by the subject will be recorded, monitored and followed-up until the resolution (or until the Investigator deems the event to be stable/chronic).

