5.3. Tolerability Assessment

Subjects' self-assessment of itching and stinging/ burning sensations during screening and treatment periods (Visits 2 through 5), skin/scalp irritation assessment by clinical site personnel (Visits 2 through 5), and ocular irritation assessment (Visits 3 through 5) by clinical site personnel will used to assess tolerability to the study treatments. Itching is defined as intense, distracting irritation or tickling sensation in the last 24 hours and is evaluated on a scale from 0 (No Itching) to 3 (Severe Itch). Stinging/ burning is defined as sensation of the skin is painfully hot or noticeable tingling sensation in the last 24 hours and is evaluated on a scale from 0 (Absent) to 3 (Severe). Skin/Scalp irritation is evaluated on a scale from 0 (None) to 3 (Severe) for four types of irritation including Pruritus= Itching, Erythema= Redness of the scalp, Excoriation= Breaking of the skin, usually caused by scratching, Pyoderma= Sores filled with clear fluid, pus or crusting. Each type of irritation is evaluated separately and its total score is recorded. Ocular irritation is evaluated for the presence of eye irritation, Conjunctivitis, and Ocular Hyperemia on a scale from 0 (No) to 1 (Yes).

Descriptive statistics using categorical methods will be used to compare tolerability measures between the test and reference treatment groups and various study days (e.g. Baseline (Visit 2), Visit 3, Visit 4, and Visit 5). Tolerability analyses will be presented for mITT and PP populations.

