5.4.1. Adverse Events

Analysis of adverse events as safety variables will be based on all adverse event (AE) capture measuring severity and frequency utilizing MedDRA terminology for consistency. AEs will be mapped to a MedDRA-preferred term and system organ classification. If a subject experiences multiple events that map to a single preferred term, the greatest severity and strongest Investigator assessment of relation to study drug will be assigned to the preferred term for the appropriate summaries. Should an event have a missing severity or relationship, it will be classified as having the highest severity and/or strongest relationship to study drug.

Summaries of treatment-emergent AEs will include any AEs reported beginning with the first dose of study drug on Day 1. The occurrence of treatment-emergent adverse events will be summarized by treatment group using preferred terms, system organ classifications, and severity. Separate summaries of treatment-emergent serious adverse events (SAEs), treatment-emergent adverse events related to study drug, and events leading to the discontinuation of study drug will be generated.

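### Safety follow-up ends when a child is found infested, so crude AE incidence and the later tolerability tables can be biased between arms: modestly for Test versus Reference, more against placebo

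*Protocol*

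**What the plan says.** Protocol section 3 makes safety a comparative aim: "The secondary objective of the study is to demonstrate the safety and local tolerability of Ivermectin 0.5% lotion compared with Sklice® 0.5% lotion". Exposure is brief: "The study drug will be applied as a single, at-home dose" (Protocol 4.1).

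Protocol 8.3 sets the AE window: "The AE reporting period for this study begins upon receiving the first application of investigational product and ends at the final protocol required visit". It does not say which visit that is for a child who fails early. For Day 2, Protocol 7.3.3 instructs: "If active lice are present on index subject, provide Standard of Care and withdraw the subject from the study". The Day 8 instruction has the same effect. Protocol 7.6 adds that for such children "their study participation will be considered complete and will be considered a treatment failure". Protocol 5.5.1 and footnote 3 of the schedule (Protocol 16.1) agree, and the schedule heads its last column as end of study or early termination. No visit or call follows a failure exit.

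On analysis, SAP 5.4.1 says: "The occurrence of treatment-emergent adverse events will be summarized by treatment group using preferred terms, system organ classifications, and severity". SAP 5.3 says: "Descriptive statistics using categorical methods will be used to compare tolerability measures between the test and reference treatment groups and various study days". SAP 3.4.2 does not impute safety data, and SAP 7 leaves missing values out of percentages. SAP 5.1 reports days on study with disposition, which is summarised by treatment group, but no safety analysis uses that variable.

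**The concern.** A child cured by the lotion is watched for about 14 days. A child who fails at Day 2 or Day 8 is watched for about 1 or 7. An arm with more failures therefore has less time in which an AE can be recorded, and a crude percentage does not show this.

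The Visit 4 and Visit 5 tolerability tables (SAP Tables 16 to 25) have a related problem. They contain only children not found infested earlier, so they describe a group selected on efficacy. Itching, pruritus and excoriation can come from the infestation itself, which makes that selection relevant to the scores.

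At stake is how a reader interprets the AE tables across the three arms and the later tolerability tables for Test against Reference.

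**Working it through.** **Inputs.** Cure rates are 67% for Test and Reference and 27% for placebo, with 120:120:40 mITT and 108:108:36 PP subjects (Protocol 10.5, SAP 3.1). Visits at Days 2, 8 and 15 are about 1, 7 and 14 days after treatment (Protocol 4.1). The documents do not say when failures are found, so that timing is assumed and varied.

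**The plan's own figure.** The documents give no figure for safety follow-up. Their power figure uses the same cure rates and is reproduced: 400,000 simulated trials with the SAP 5.2.2 interval and continuity-corrected Z-tests gave 81.5% joint power, against the stated minimum of 80%. The sample size is not in question here.

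**Mean observation.** Mean days = p × 14 + (1 − p) × m, where p is the cure rate and m is the mean exit time of failures.

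- All failures at Day 2, m = 1. Active: 0.67 × 14 + 0.33 × 1 = 9.71. Placebo: 0.27 × 14 + 0.73 × 1 = 4.51.
- Split 50/25/25 over Days 2, 8 and 15, m = 0.5 × 1 + 0.25 × 7 + 0.25 × 14 = 5.75. Active: 9.38 + 0.33 × 5.75 = 11.28. Placebo: 3.78 + 0.73 × 5.75 = 7.98.
- All failures at Day 15, m = 14: 14 days in every arm, no gap.

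**Test versus Reference.** With equal p and equal m the gap is zero. To bound it when equivalence is met, take Reference at 72/108 = 0.6667 in PP and find the lowest Test count that passes the SAP interval. At 64/108 = 0.5926:

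- se = √[(0.5926 × 0.4074 + 0.6667 × 0.3333)/108] = 0.0655
- L = −0.0741 − 1.645 × 0.0655 − 1/108 = −0.191, which passes.

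At 63/108, L = −0.201, which fails. The largest shortfall is thus 7.4 points. The gap is 0.0741 × (14 − 1) = 0.96 day if all failures are found at Day 2, or 0.0741 × (14 − 5.75) = 0.61 day with the split. PP counts serve here as a guide to the Safety population.

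**Effect on crude AE incidence.** Assume a true 14-day risk of 10% in every arm and all failures at Day 2, the worst case. If risk is even over 14 days, a failure shows 10%/14 = 0.71%. The 7.4-point shortfall then produces 0.0741 × (10 − 0.71) = 0.7 percentage point. The 95% half-width for 10% versus 10% at 120 per arm is 1.96 × √(2 × 0.1 × 0.9/120) = 7.6 points.

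For active versus placebo, the crude incidence depends on how much of the risk falls in the first day:

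| Share of risk in first day | Active (67%) | Placebo (27%) |
|---|---|---|
| 1/14 (even) | 6.9% | 3.2% |
| 80% | 9.3% | 8.5% |
| 100% | 10.0% | 10.0% |

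**Who reaches Day 15.** If all failures are found at Day 2, 67% of active and 27% of placebo children reach it. With the split, the shares are 1 − 0.33 × 0.75 = 75% and 1 − 0.73 × 0.75 = 45%.

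**Would a rate per subject-day repair it?** Take 80% of risk in the first day, all failures at Day 2, and 67% versus 47% cure. Crude incidence is 0.67 × 10 + 0.33 × 8 = 9.34% versus 0.47 × 10 + 0.53 × 8 = 8.94%, a ratio of 0.96. Mean days are 9.71 and 7.11, so the daily rates are 0.96% and 1.26%, a ratio of 1.31. The rate produces a larger artefact in the opposite direction.

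**The case against.** The strongest reply is that the effect on the stated objective is small. The plan assumes equal cure rates. A true 20-point deficit would give a gap of 2.6 days (9.71 − 7.11), but that lies on the equivalence margin, where the design concludes equivalence at most about 5% of the time. Safety reporting is descriptive. SAP 5.1 will show days on study by arm, and SAP 7 requires each summary to show how many subjects contribute. All of this stands and limits the size of the point. It does not remove it: showing unequal follow-up does not correct for it.

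A reader might infer from Protocol 8.3 alone that AE collection stops when lice are seen. It does not say so; the cut-off follows from 8.3 read with 5.5.1, 7.3.3 and 7.6. Under Protocol 8.1, AEs already recorded are followed until resolved or stable, but this does not solicit new ones. Protocol 8.3 ties SAE capture to the period of participation, although nothing bars recording a later spontaneous report. Protocol 5.6 calls for a discontinuation visit on withdrawal, but schedules no contact after it.

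A reader might also infer that the weaker product must look better tolerated. The documents do not support that for itching, pruritus and excoriation. Children found infested at Day 2, 8 or 15 are still scored at that visit, so more failures can also raise scores there. Only their later visits are lost.

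Finally, the Protocol synopsis and 7.1.1 base tolerability on all follow-up visits. A change that dropped the later visits would depart from this, so they should stay.

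**Conclusion.** The point holds as a modest, avoidable bias. Efficacy sets the safety window, and the SAP's crude summaries do not allow for it.

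For Test versus Reference the gap in mean follow-up is nil with equal cure rates and failure timing. It is under about 1 day if equivalence is met with Reference at 72/108. The worst-case AE artefact is then about 0.7 point, assuming 10% risk spread evenly, well inside a half-width of 7.6 points. It would be wrong to conclude that the Test-Reference safety objective is undermined; the comparison can be biased if cure rates differ.

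Active versus placebo is more affected: 9.7 versus 4.5 days, or 11.3 versus 8.0 with the assumed split. Placebo is watched least, so the active lotions could look less safe than they are. SAP 5.3 plans no formal tolerability comparison with placebo, but the AE summaries cover all three arms.

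These sizes rest on the plan's cure rates and on assumed failure timing and AE timing. If all failures are found at Day 15, or all AEs fall in the first day, the AE bias vanishes.

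**What to change.** 1. SAP 5.4: add a TEAE summary by arm restricted to onset up to Visit 3 (Day 2), the common window before any failure exit. SAP 5.3: present Visit 3 as the tolerability comparison unaffected by failure exits, and keep the other visits.
2. SAP 5.3 and the Visit 4 and 5 parts of Tables 16 to 25: label them 'subjects not found infested at an earlier visit' and show the number assessed per arm.
3. Protocol 8.3: state that for early failures the AE reporting period runs to Day 15, collected by one telephone contact, with AEs after rescue listed separately.

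Do not add a rate per subject-day as the remedy; after a single application with early risk it can mislead more than the crude figure.

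Cost: a few tables and about 80 to 110 calls. If all failures are found before Day 15, the number is 240 × 0.33 + 40 × 0.73 = 108; with 75% found before then, it is 81. AEs after rescue are confounded by the over-the-counter product, hence the separate listing. The withdrawal rule, primary endpoint and sample size are unchanged.

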8.4 Reporting Procedures

8.4.1 Adverse Event Reporting

8.4.2 Serious Adverse Event Reporting

In the event of a SAE, whether related to study drug or not, the Investigator or representative must make an accurate and adequate report consisting of at least the minimum criteria (Site and Subject ID, Date site became aware of the event, SAE Term, Seriousness criteria, Study Drug information, Investigator/Reporter and site address) within 24 hours by email, fax, or telephone to Biorasi Safety and Pharmacovigilance team. Biorasi Safety and Pharmacovigilance team will complete the SAE report onto a MedWatch 3500A form for evaluation and convey for review by the Medical Monitor and Sponsor contact. Accurate Completion of the MedWatch 3500A form will consist of all data supplied such as Subject's demography, SAE narrative, concomitant medication, laboratory parameters and relevant medical history.

In addition, if required by the applicable IRB/IEC, the Investigator will submit the SAE reports to the IRB/IEC within 15 calendar days of discovering the SAE, or alternatively, within accordance of applicable regulations or IRB/IEC requirements.

Copies of each report with the associated documentation (i.e., queries, medical records, lab records, IRB/IEC communications and all source documents) will be kept in the site's study file.

A subject experiencing one or more SAEs will receive treatment and follow-up evaluations by the Investigator or may be referred to another appropriate physician for treatment and follow-up. The Investigational Site will be responsible for collection and forwarding follow-up SAE information to the Biorasi Safety and Pharmacovigilance.

MEDICAL MONITOR

[name]
Biorasi Safety and Pharmacovigilance
E-mail: [contact]
[name]

[contact]

